4.2.1 Instructions for Delays in Dosing

Dosing delays in study drug (masked ataluren or placebo) administration should adhere to the following guidelines:

- If dosing of study drug is delayed by ≤ 1 hour, the planned dose should be taken with no changes to the subsequent dose schedules;
- If study drug dosing is delayed by > 1 hour but ≤ 4 hours, the planned dose should be taken; however, all future doses for that day should be shifted later by an approximately corresponding amount;
- If study drug dosing is delayed by > 4 hours, the dose should not be taken. Study drug administration may continue but the missed dose should not be taken and the planned timing of subsequent study drug dosing should not be altered.

4.2.2 Study Drug Preparation and Storage

Study drug sachets should be stored at room temperature, away from the reach of children until time of reconstitution and should only be opened at the time of dose preparation. The full contents of each sachet should be mixed with at least 30 mL (1 ounce) of liquid (water, milk, fruit punch), or 3 tablespoons of semi-solid food (yogurt or applesauce). The prepared dose should be mixed well before administration. The amount of the liquid or semi-solid food can be increased based on subject preference.

Each prepared dose is best administered immediately after preparation. The prepared dose should be discarded if not consumed within 24 hours of preparation if kept refrigerated (2°C – 8°C), or within 3 hours at room temperature (15°C – 30°C).

The clinic staff will instruct each subject or caregiver on the specific number of sachets to be taken from each kit for each dose and will provide detailed oral directions regarding drug preparation. In addition, detailed written drug mixing and dosing instructions will be provided to the subject or caregiver when drug supplies are dispensed.

4.3 Method for Assigning Subjects to Treatment Groups

This interventional study contains a placebo portion where subjects will not receive active drug therapy beyond the existing background AED regimen. The allocation of ataluren and placebo to treatment number will be completed according to a masked randomization schedule.

Randomization is an accepted means to reduce bias and allows for the highest standard of evidence in documenting a treatment effect. The permuted block randomization technique will be used. Such a method allows the treatment groups to be balanced with respect to the predefined stratification factors as well as for the number of subjects in each arm. The process will be established and performed by experienced clinical research organizations to maximize the integrity and security of the randomization and ensure appropriate access and convenience-of-use by the investigational sites. The method should be sufficient to preclude site personnel from making inferences regarding treatment assignments based on known block sizes. A 1:1 randomization of ataluren to placebo is planned in order to avoid the loss of statistical power associated with an unbalanced randomization.

To minimize the potential compromise of study drug masking and to reduce the chance of inadvertent dosing errors or intentional attempts to mix active drug and placebo within families, if the case occurs, the randomization system will allocate subsequently enrolled family members (eg, siblings) to the same treatment group as the first family member enrolled. There is past precedence for this approach.

When a subject is randomized in the study and is ready to begin study drug, the Principal Investigator or qualified designee will dispense the appropriate quantity of masked study medication and distribute it to the subject and/or subject's caregiver. Extensive instructions on the correct dosage administration and schedule will be discussed and fully understood prior to leaving the appointment.

4.4 Subject Compliance Monitoring

The study team will assess and track subject compliance with the study drug regimen via clinical evaluations and follow-up email or phone calls. The subjects will be seen for clinical evaluations every month for up to the next 10 months on study drug regimen.

Any subject who is significantly non-compliant with the study drug regimen (< 80% or > 120%) will be withdrawn from the study as per the Principal Investigator.

4.5 Prior and Concomitant Therapy

Throughout the study, including during the Treatment Periods with study drug administration, subjects will continue their current AED regimen consisting of 1 to 3 drugs at stable doses for at least 4 weeks prior to the Screening Visit. Concomitant AED concentrations will be collected at the Baseline Visit and during the study to assess for the potential interactions. If the subject has a VNS, the settings must be on stable settings for a minimum of 3 months prior to the Screening Visit. In addition, if the subject is on a ketogenic diet, a stable ratio must be present for at least 3 months prior to the Screening Visit. All concomitant AEDs are permitted during the randomized portion of the study; felbamate is allowed if the subject has been on a stable dose for ≥ 12 months prior to the Screening Visit. Epidiolex will be allowed as a concomitant AED as it has received FDA approval. Medication adjustments will be avoided, if possible, and may require the subject to exit the study at the discretion of the investigator. Medication adjustments and changes will be allowed in the open label portion of the study.

4.6 Receiving, Storage, Dispensing, and Return

4.6.1 Receipt of Drug Supplies

Study drug (ie, masked ataluren and masked placebo) will be shipped to the site of the Principal Investigator at NYU from PTC Therapeutics, via FedEx.

Upon receipt of the study drug supplies, an inventory will be performed and a drug receipt log filled out and signed by the person accepting the shipment. The designated study staff will count and verify that the shipment contains all the items noted in the shipment inventory. Any damaged or unusable study drug in a given shipment (active drug or comparator) will be documented in the study files. The investigator will notify PTC Therapeutics of any damaged or unusable study drugs that were supplied to the investigator's site.

4.6.2 Storage

Sachets containing study drug will be stored at controlled room temperature (15°C–30 °C) in a locked room accessible only to study personnel. The available stability data from representative samples support the use of the drug product for 48 months when stored at room temperature. The stability of the clinical study samples or representative samples may be monitored, as appropriate, to support the clinical study.

4.6.3 Dispensing of Study Drug

Dosing of ataluren will be based on mg/kg of subject body weight and will be adjusted to allow for dosing with up to 3 of the available sachet dose strengths (125 mg, 250 mg, and/or 1000 mg). The entire contents of the sachet will be constituted with the constitution medium and will be administered. Supply of study drug will be calculated based on subject weight and will be provided by the Principal Investigator or qualified designee. Quantity of study drug sachets distributed to each study subject will be noted in a study log upon dispensation. Regular study drug reconciliation will be performed to document drug assigned and drug remaining. This reconciliation will be logged on the drug reconciliation form, and signed and dated by the study team.

4.6.4 Study Drug Accountability, Return and Destruction of Study Drug

Study personnel must ensure that all study drug supplies are kept in a temperature-monitored, secure, locked area with access limited to authorized personnel. Study product must not be used outside the context of this protocol. Under no circumstances should the investigator or site personnel supply study product to other investigators or clinics, or allow the supplies to be used other than as directed by this protocol.

The investigator and/or the responsible site personnel must maintain accurate records of the receipt of all study drug shipped by PTC Therapeutics or its designee, including, but not limited to, the date received, lot number, amount received, and the disposition of all study drug. Current dispensing records will be maintained that include the date and amount of drug dispensed, relevant kit and sachet numbers, and subject's assigned study number.

Subjects and/or caregivers should return all remaining study drug (all unused sachets) to the study site at each onsite study visit. A Subject Study Drug Accountability Log will serve as the source document for drug supply to the subjects and will document the return of any unused drug for compliance assessments.

A final reconciliation of drug shipped, drug consumed, and drug remaining will be completed at the completion of the study. Any discrepancies noted will be investigated, resolved, and/or documented prior to destruction of unused study drug.

Unused clinical supplies will be destroyed or returned to PTC Therapeutics or its designee, as per investigator/PTC Therapeutics agreement. Records documenting the date of study drug destruction or shipping, relevant sachet numbers, and amount shipped (or destroyed) should be kept in the investigator site study file.

4.6.5 Overdose Precautions

For any subject experiencing an overdose (administration of an ataluren dose > 4 times the intended total daily dose level for this protocol [ie, > 160 mg/kg/day]), observation for any symptomatic side effects should be instituted, and vital signs and biochemical and hematological parameters should be followed closely (consistent with the protocol or more frequently, as needed). Appropriate supportive management to mitigate adverse effects should be initiated. Pending the acquisition of sufficient human experience with the drug, use of gastric lavage or induction of emesis is not specifically recommended nor contraindicated. The Principal Investigator must be contacted if an overdose occurs and the overdose must be reported as an AE according to Section 8.5 (or as an SAE if the overdose meets the applicable criteria for an SAE). The Principal Investigator is responsible for reporting the information to PTC Therapeutics.

4.6.6 Inadvertent Exposure and Spill Precautions

Reference can be made to the IB for current information on inadvertent exposures and spill precautions.

5 SAFETY MONITORING AND STUDY DRUG TREATMENT MODIFICATION

5.1 Laboratory Abnormalities and Adverse Events Requiring Evaluation and Potential Drug Interruption/Modification

Subjects must be monitored closely for AEs or laboratory abnormalities during the course of the study.

For AEs or laboratory abnormalities, the investigator will use judgment in determining whether the event or abnormality is clinically significant, whether diagnostic evaluation is warranted, and whether potential interruption of study drug treatment is appropriate. In general, life-threatening (Grade 4) or severe (Grade 3) AEs or laboratory abnormalities should be considered clinically significant, although recurrent or persistent moderate events (Grade 2) may also be considered clinically significant in certain circumstances. Reference should be made to the Common Terminology Criteria for Adverse Events (CTCAE), Version 4.1 (see http://evs.nci.nih.gov/ftp1/CTCAE/CTCAE_4.03_2010-06-14_QuickReference_5x7.pdf) for grading the severity of AEs and laboratory abnormalities.

5.1.1 Evaluation of Adverse Events or Laboratory Abnormalities

The Principal Investigator ([name]) or designee should be notified of any AE or laboratory abnormality that leads to dose interruption and should be apprised of ancillary laboratory or other diagnostic findings and the evolving data from any work-up of the initial abnormality.

Clinical evaluations for potential hepatic and renal toxicities may include the following:

- **Hepatic:** The medical history, hepatitis screening results, all clinical blood values (particularly serum bilirubin, gamma-glutamyl transferase, aspartate aminotransferase, and alanine aminotransferase values), and all concomitant medications should be reviewed. Depending upon changes observed, the recommended diagnostic workup may include more frequent monitoring or further evaluations for viral hepatitis and immune disorders; tests for cholelithiasis; or abdominal ultrasound, computed tomography (CT), magnetic resonance imaging (MRI), or other imaging methods.
- **Renal:** The medical history, all clinical blood and urine renal values, serum electrolytes, medications, and potential pre- or post-renal conditions should be reviewed. Depending upon the changes observed, recommended diagnostic workup may include further evaluations of blood or urine; tests of glomerular filtration rate, concentrating ability, or other renal functions; CT, MRI, or other imaging methods; and/or renal biopsy.
- Elevation of aspartate aminotransferase or alanine aminotransferase to $> 3\times$ baseline will lead to repeat laboratory studies and if these remain elevated, to a reduction in study medication and repeat laboratory studies. No other significant toxicities have been reported with ataluren, and elevated liver function studies are rare.

5.1.2 Instructions for Resuming Study Drug Administration after an Interruption for Safety Concerns

In deciding whether to re-institute study drug after a dose interruption due to any clinically significant safety concern, the investigator should consider factors such as the following (and may confer with the appropriate personnel at PTC Therapeutics if needed):

- Type and severity of the AE or laboratory abnormality
- The potential causal relationship of study drug
- The subject's status in terms of epileptic seizures (frequency and types) and other health conditions
- The ability to monitor for recurrence of the event

If further evaluation reveals that the AE that led to dose interruption was not related to the study drug, study drug may be restarted.

If the subject experiences a recurrence of a previous abnormality that led to study drug dose interruption or experiences the new occurrence of an unacceptable AE or laboratory abnormality, the investigator will interrupt study drug and may confer with the appropriate personnel at PTC Therapeutics if needed regarding the potential need to discontinue study drug permanently.

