1.5.1 Drug Administration Plan

Subjects will receive 12 weeks of ataluren or placebo during each treatment period. Treatment Period 1 will be followed by a 4-week Washout Period. Based on ataluren PK and pharmacodynamic data, the 4-week washout period is deemed an appropriate length of time to eliminate any ataluren drug effects. Following the Washout Period, subjects will crossover to receive the opposite treatment during Treatment Period 2 as follows:

- Subjects receiving ataluren during Treatment Period 1 will receive placebo during Treatment Period 2.
- Subjects receiving placebo during Treatment Period 1 will receive ataluren during Treatment Period 2.

Study drug will be administered 3 times per day (TID). The dose level to be administered is: 10 mg/kg in the morning, 10 mg/kg at midday, and 20 mg/kg in the evening.

Dosing will be based on the subject's body weight at Baseline. Weight will be assessed at every clinic visit. If the subject's body weight changes by $\geq 10\%$ from Baseline, the actual dose may be re-calculated.

The first dose of study drug will be administered in the clinic and the date and time of administration will be recorded. At the end of each Treatment Period, the last dose of study drug will be taken on the evening before the clinic visit (ie, the night before the Visit 4/Week 12 [end of Treatment Period 1] and the night before Visit 7/Week 28 [end of Treatment Period 2]).

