3.6 Early Withdrawal of Subjects

3.6.1 When and How to Withdraw Subjects

A subject may be discontinued from study drug at any time if the subject, subject's legal guardian, or the investigator feels that it is not in the subject's best interest to continue (see also Section 7). The following is a list of possible reasons for study drug discontinuation:

1. Parental/legal guardian withdrawal of consent.
2. Subject is not compliant with study procedures.
3. Protocol violation requiring discontinuation of study drug.
4. Severe adverse events, including significant toxicity such as severe cognitive or behavioral toxicity, impaired liver and renal function, or impaired hematopoiesis.
5. Seizure exacerbation not attributable to other known provocative factors.
6. Interaction with concomitant AED regimen that leads to unacceptable toxicity. Medication adjustments will be avoided, if possible, and may require the subject to exit the study, at the discretion of the Investigator.

Specific drug-related toxicities will be assessed and managed by the Principal Investigator.

Depending on the nature of the signs (eg, changes in serum chemistries, liver function tests) or symptoms (eg, rash), the subject will be assessed to determine the severity and likelihood of relation to study medication. Based on this assessment, the medication may be discontinued, the dose may be reduced, or the drug may be continued with ongoing assessment. If the study drug is discontinued due to a suspected toxicity, it will only be restarted if there is strong evidence that the toxicity was likely not related to the study medication (eg, liver tests were elevated due to a cytomegalovirus infection).

If a subject must discontinue study drug, the method for discontinuation from study drug will be determined based on the type of reaction and/or reason for withdrawal. For example, if the subject experiences a rapidly progressive rash, it would lead to abrupt cessation of study drug,

but if subject experiences excess tiredness, study drug may be tapered off. A discussion of the method of cessation will occur between the subject and/or subject's parent/legal guardian and the physician.

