6 SCHEDULE OF EVENTS AND STUDY PARAMETERS

6.1 Schedule of Events

The types and timing of data to be recorded are summarized in Table 1.

Table 1 Schedule of Events

Protocol Activities	Screening ^a	Treatment Period 1			4-Week Washout/ Crossover	Treatment Period 2 ^b		EOS Visit ^c or Begin Open- Label	Open-Label Extension ^d			End of Treatment	Follow Up ^e
		0	6	12		16	22		28	52	76		
Week (±6 days)	-4 (Wk -4 to Wk 0; Day -28 to Day 1)	0	6	12		16	22	28	52	76	100	124	128
Visit	1	2 ^f	3	4		5	6	7	8 ^g	9	10	11	12
Informed consent/assent	X												
Medical history	X												
Serum viral screen	X												
Physical examination	X	X		X		X		X	X	X	X	X	X
Height and weight	X	X	X	X		X	X	X	X	X	X	X	X
Vital signs	X	X	X	X		X	X	X	X	X	X	X	X
Seizure data diary provided	X	X	X	X		X	X	X	X	X	X	X	
Seizure data diary collected		X	X	X		X	X	X	X	X	X	X	X
Study drug dispensed		X ^h	X			X ^h	X	X ^h	X ^h	X ^h	X ^h		
Study drug administration		X ⁱ				X ⁱ		X ⁱ					
Study drug compliance and return			X	X			X	X	X	X	X	X	
Adverse events	X	X	X	X		X	X	X	X	X	X	X	X
Concomitant medications	X	X	X	X		X	X	X	X	X	X	X	X

Protocol Activities	Screening ^a	Treatment Period 1			4-Week Washout/ Crossover	Treatment Period 2 ^b		EOS Visit ^c or Begin Open- Label	Open- Label Extension ^d			End of Treatment	Follow Up ^e
		0	6	12		16	22		28	52	76		
Week (±6 days)	-4 (Wk -4 to Wk 0; Day -28 to Day 1)	0	6	12		16	22	28	52	76	100	124	128
Visit	1	2 ^f	3	4		5	6	7	8 ^g	9	10	11	12
Blood for CBC, CMP, LFTs, BUN, creatinine levels, serum HCG ^j	X	X		X		X		X	X	X	X	X	
Blood for plasma PK for ataluren ^k			X			X	X						
Blood for plasma PK for AED assessment ^l		X	X			X	X	X	X			X	
Urinalysis	X	X		X		X		X	X	X	X	X	
Behavior Assessment System for Children		X		X		X		X				X	
Vineland Adaptive Behavior Scales		X		X		X		X				X	
Quality of Life in Childhood Epilepsy		X		X		X		X				X	

Abbreviations: AED = antiepileptic drug; BUN = blood urea nitrogen; CBC = complete blood count; CMP = comprehensive metabolic panel; EOS = end of study; EOT = End of treatment; F/U = follow-up; HCG= human chorionic gonadotropin; LFTs = liver function tests; PK = pharmacokinetics; wk = week

a. Screening will occur from Week -4 to Week 0 (ie, 28 days). The ±6 day visit window is not applicable to the Screening Period.

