b. During Treatment Period 2, subjects will crossover and begin receiving masked study drug opposite of what they received during Treatment Period 1 (ie, subjects previously receiving masked ataluren will now receive placebo and subjects previously receiving placebo will now receive ataluren).

01 Aug 2019

- c. The EOS visit (Week 28) will be completed for all subjects who complete or discontinue early from Treatment Period 1 and 2. Subjects who complete the EOS visit may continue in the open-label portion of the study at Week 28, otherwise a follow-up visit should be scheduled after 4 weeks.
- d. All subjects enrolling in the open-label extension study will receive ataluren 10, 10, 20 mg/kg 3 times per day for 96 weeks.
- e. The Follow-up visit is to occur 4 weeks after the last dose of study drug, regardless of whether the subject discontinues prematurely or completes the EOS visit and/or the open-label extension.
- f. Visit 2 is considered the Baseline Visit. Visit 2 must occur no sooner than 28 days and up to 42 days after Visit 1. All study and laboratory assessments must be completed prior to the first dose of study drug administration.
- g. If the subject begins but does not complete the open-label extension, complete EOT (Week 124).
- h. The first dose of study drug should be given in the clinic at Visit 2 (Baseline), Visit 5 (Week 16), and, if applicable, in the open-label extension at Visit 7 (Week 28).
- i. The last dose of study drug prior to Visit 4/Week 12 (Treatment Period 1) and Visit 7/Week 28 (EOS Visit) should be taken the night before, at home. No morning dose should be taken prior to the clinic visit.
- j. Serum HCG samples taken only for female subjects of childbearing potential
- k. Ataluren plasma PK will be assessed at 0 hr (pre-dose) at Visit 5/Week 16 and at 0 hr (pre-dose) and 2 hr post-dose at Visit 3/Week 6 and Visit 6/Week 22.
- l. AED plasma PK will be assessed at 0 hr (pre-dose of AED, including but not limited to valproate, clonazepam, lamotrigine, topiramate, and levetiracetam).

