6.1.1.3 Visit 3 (Week 6)

The subject will return to the site for Visit 3. Procedures at Visit 3 will proceed as follows:

- Height and weight
- Vital signs (including systolic and diastolic blood pressure, radial pulse rate, and body temperature): performed after the subject has been in a sitting position for 3–5 minutes

- Collect seizure diary and review entries
- Record any AEs occurring since last visit and any that occur during this visit
- Record any changes in concomitant medications
- Blood draw for plasma PK of ataluren (0 hr, pre-dose, and 2 hr post-dose)
- Blood draw for plasma PK AED level assessment (0 hr, pre-dose)
- Dispense new seizure diary and review instructions for completion
- Review returned study drug and compliance
- Dispense masked study drug and review administration instructions
 - TID dosing 10 mg/kg, 10 mg/kg, 20 mg/kg (morning, midday, evening)
- Instruct subject to return in 6 weeks for Visit 4

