6.1.1.6 Visit 6 (Week 22)

The subject will return to the site for Visit 6. Visit 6 will proceed as follows:

- Height and weight
- Vital signs (including systolic and diastolic blood pressure, radial pulse rate, and body temperature): performed after the subject has been in a sitting position for 3–5 minutes
- Collect seizure diary and review entries
- Record any AEs occurring since last visit and any that occur during this visit
- Record any changes in concomitant medications
- Blood draw for plasma PK of ataluren (0 hr, pre-dose and 2 hr post-dose)
- Blood draw for plasma PK AED level assessment (0 hr, pre-dose)

- Dispense new seizure diary and review instructions for completion
- Review returned study drug and compliance
- Dispense masked study drug and review administration instructions
 - TID dosing 10 mg/kg, 10 mg/kg, 20 mg/kg (morning, midday, evening)
- Instruct subject to return in 6 weeks for Visit 7

6.1.1.7 Visit 7 (Week 28 – EOS Visit [or Early Termination Visit])/Start of Open-Label Extension Study

The subject will return to the site for Visit 7. This visit will be considered the EOS visit and should be completed for all subjects. Subjects should have taken their final dose of study drug the night before the clinic visit.

Additionally, any subject who discontinues early from the study should complete this visit.

Visit 7 will proceed as follows:

- Physical examination
- Height and weight
- Vital signs (including systolic and diastolic blood pressure, radial pulse rate, and body temperature): performed after the subject has been in a sitting position for 3–5 minutes
- Collect seizure diary and review entries
- Record any AEs occurring since last visit and any that occur during this visit
- Record any changes in concomitant medications
- Blood draw plasma PK for AED level assessment (0 hr, pre-dose)
- Complete the following QOL assessments:
 - Behavior Assessment System for Children
 - VABS-II
 - QOLCE
- Blood draw for clinical laboratory evaluations
 - CBC, CMP, LFTs, BUN, creatinine, serum HCG
- Urinalysis
- Review returned study drug and compliance
- If subject is enrolling in the open-label extension study, dispense new seizure diary and review instructions for completion
- No study drug will be dispensed at this visit if the subject is not enrolling in the open-label extension study.
- If the subject is enrolling in the open-label extension study, open-label study drug will be dispensed to the subject.

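### No scheduled liver, renal or hematology test falls between the first and last dose of either masked period, so within a period the AST/ALT rule in 5.1.1 depends on unscheduled testing

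*Combined protocol and SAP*

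**What the plan says.** **The rule.** Section 5.1.1 provides that AST or ALT above 3 times "baseline will lead to repeat laboratory studies and if these remain elevated, to a reduction in study medication and repeat laboratory studies". The wording is mandatory, and it is not limited to scheduled samples. Section 3.6.1 lists possible reasons for stopping study drug, among them significant toxicity such as "impaired liver and renal function, or impaired hematopoiesis". Section 5.1 requires close monitoring for laboratory abnormalities during the study but fixes no dates.

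**The schedule.** The Table 1 row "Blood for CBC, CMP, LFTs, BUN, creatinine levels, serum HCG" is marked at Screening and at Weeks 0, 12, 16, 28, 52, 76, 100 and 124. It is blank at Weeks 6 and 22. The visit lists in 6.1.1 agree with the table.

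**Timing against dosing.**
- Week 0: the Table 1 note on Visit 2 says "All study and laboratory assessments must be completed prior to the first dose of study drug administration".
- Weeks 12 and 28: Section 1.5.1 says that "the last dose of study drug will be taken on the evening before the clinic visit", and a Table 1 note rules out a dose that morning. No drug is dispensed at Week 12 (6.1.1.4).
- Week 16: the first Period 2 dose is given in clinic after all other procedures (6.1.1.5).
- Week 6: the blood work in 6.1.1.3 is "Blood draw for plasma PK of ataluren (0 hr, pre-dose, and 2 hr post-dose" and "Blood draw for plasma PK AED level assessment (0 hr, pre-dose". Section 6.1.1.6 lists the same two items for Week 22. More masked drug is dispensed at both visits.

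At Week 28, Section 6.1.1.7 adds: "If the subject is enrolling in the open-label extension study, open-label study drug will be dispensed to the subject".

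**The concern.** A rule that requires a dose reduction needs a result to act on while drug is being taken. Here the routine results come just before each masked period starts or just after it ends. A rise that develops during Period 1 is first seen, on the schedule, when there is no study drug to reduce. A rise during Period 2 is first seen when masked treatment is over. The laboratory-based stopping reasons in 3.6.1 have the same gap.

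The subjects are children aged 2 to 12 on 1 to 3 AEDs. Section 1.5.2.1 says that ataluren may raise the levels of some co-medications to the point of toxicity, and for that reason places AED level checks at Weeks 6 and 22. The safety panel was not placed at those visits. What is at stake is the chance to act on an abnormality within the period in which it arises.

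**Working it through.** No sample size, power or alpha figure is involved, and the plan states no figure to reproduce. The check sets the laboratory row of Table 1 against the dosing days.

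**Inputs.** Laboratory weeks up to Week 28: -4, 0, 12, 16, 28 (Table 1). Masked dosing: Weeks 0 to 12 and 16 to 28 (1.5), with the last dose on the evening before the Week 12 and Week 28 visits (1.5.1, 4.2). Visit window: ±6 days (Table 1).

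**Dosing days, counting the Week 0 dose as day 0.**
- Period 1: first dose on day 0 after the draw. Last dose on the evening of day 12 × 7 − 1 = 83.
- Period 2: first dose on day 16 × 7 = 112 after the draw. Last dose on the evening of day 28 × 7 − 1 = 195.

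| Visit | Day | Position in dosing | Safety panel |
|---|---|---|---|
| Week 0 | 0 | before first Period 1 dose | yes |
| Week 6 | 42 | during Period 1 | no |
| Week 12 | 84 | morning after last Period 1 dose | yes |
| Week 16 | 112 | before first Period 2 dose | yes |
| Week 22 | 154 | during Period 2 | no |
| Week 28 | 196 | morning after last Period 2 dose | yes |

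**Count.** Scheduled panels between first and last dose: 0 in Period 1 and 0 in Period 2, so 0 over 12 + 12 = 24 weeks of masked dosing.

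**Length of each gap.** 12 × 7 = 84 days. Holding the first-dose day fixed and moving the end-of-period visit by 6 days gives 84 − 6 = 78 to 84 + 6 = 90 days. Section 4.2 gives 90 days as the length of a period, which is the upper end. Moving the visit cannot put the draw on a dosing day, because the last dose is tied to the evening before the visit.

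**Does another passage supply an on-drug test?**
- 5.1 sets a general duty to monitor, without dates.
- 5.1.1 allows more frequent hepatic monitoring, but only depending on changes already observed, so it cannot find the first one.
- 3.6.1 allows a reduction after assessment of signs that include liver tests, but schedules no test.
- 4.4 mentions monthly clinical evaluations. These do not appear in Table 1, and no laboratory test is named.

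None fixes one. In the open-label extension, panels fall during dosing at Weeks 52, 76 and 100, with a further panel at Week 124, so the rule has scheduled results there.

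**The case against.** The strongest reply is that nothing contradicts anything: 5.1.1 says what to do if an elevation is found, Table 1 says when routine blood is drawn, and both can be followed as written. Section 1.5.3 says that visits and blood sampling were kept low for these children, and 5.1.1 calls raised liver tests rare. Part of this stands, since the text and table do agree. But blood is already drawn at Visits 3 and 6, so the aim of few draws does not explain why the panel is absent there. Rarity did not stop the plan from making the rule mandatory.

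Four stronger readings are tempting, and the documents do not support them.
- *The rule cannot act in the masked phase.* It applies to any AST/ALT result. Unscheduled tests are allowed, and 7.6.1 accepts results from other laboratories for AE reporting. A persistent Week 12 or 16 elevation could affect Period 2 drug, although the child has by then crossed to the opposite treatment. A Week 28 result could affect open-label drug.
- *There is no on-treatment laboratory value for the safety objective.* The Week 12 and 28 draws follow the last evening dose by about the 12 hours that 4.2 sets between evening and morning doses. They are sound end-of-treatment values for the summaries in 7.6.2. What is missing is a value within the period.
- *This is the only numeric dose-modification rule.* Section 1.5.1 has a weight-based recalculation at a change of 10% or more, and 5.2 has a 50% step before discontinuation.
- *The first test on continuing ataluren is at Week 52.* A placebo-first child who enters the extension goes from Period 2 ataluren into open-label ataluren at Week 28, and the Week 28 panel falls within that exposure.

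**Conclusion.** The mismatch is real and should be resolved. In each masked period a child has about 12 weeks of dosing (78 to 90 days) with no scheduled liver, renal or hematology test. Within that time, the mandatory AST/ALT rule and the laboratory-based stopping reasons rest entirely on unscheduled testing. The weakness lies in acting in time; the end-of-period description of laboratory safety is not undermined.

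This rests on reading Table 1 and the visit lists as the full set of planned draws, and on the last dose being taken the evening before Weeks 12 and 28 as stated. The practical gain is bounded. Section 7.1 says that enrolment has stopped, and the documents do not say how many children remain in masked treatment; there may be none. No view is taken on the threshold, on any dose, or on the clinical rule itself.

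**What to change.** Reconcile 5.1, 5.1.1 and 3.6.1 with Table 1, 6.1.1.3 and 6.1.1.6, so that the schedule supplies the results that the rule uses while masked drug is being taken. How to do so is for the sponsor and investigator to decide. Visits 3 and 6 already include a blood draw and fall within dosing. If the schedule changes, update the blood volumes in 6.3 (about 8 to 20 mL at most per visit, about 70 mL in total). If it stays as it is, 5.1.1 should say that within a masked period the rule depends on unscheduled tests. For periods already completed, the study report should state the same limitation.

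The cost is an amendment to one table row and two visit lists and, if panels are added at existing draws, a few mL more blood and a routine panel each time. The benefit in the masked phase is limited to children still in it.
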